12. MEASUREMENT OF EFFECT

Although the clinical benefit of these drugs has not yet been established, the intent of offering this treatment is to provide a possible therapeutic benefit, and thus the patient will be carefully monitored for tumor response and symptom relief in addition to safety and tolerability. Patients with measurable disease will be assessed by standard criteria. For the purposes of this study, patients should be re-evaluated every 8 weeks. In addition to a baseline scan, confirmatory scans (CT or MRI) will also be obtained 8 weeks (+/- 7 days), following initial documentation of an objective response.

12.1 Antitumor Effect – Solid Tumors

For the purposes of this study, patients should be re-evaluated for response every 8 weeks. In addition to a baseline scan, confirmatory scans should also be obtained 8 weeks following initial documentation of objective response.

Response and progression will be evaluated in this study using the new international criteria proposed by the revised Response Evaluation Criteria in Solid Tumors (RECIST) guideline (version 1.1) [Eur J Ca 45:228-247, 2009]. Changes in the largest diameter (unidimensional measurement) of the tumor lesions and the shortest diameter in the case of malignant lymph nodes are used in the RECIST criteria.

12.1.1 Definitions

Evaluable for toxicity. All patients will be evaluable for toxicity from the time of their first treatment with study treatment.

Evaluable for objective response. Only those patients who have measurable disease present at baseline, have received at least three cycle of therapy, and have had their disease re-evaluated post-baseline will be considered evaluable for response. These patients will have their response classified according to the definitions stated below. Patients who exhibit objective disease progression prior to the end of Cycle 1 will also be considered evaluable.

Evaluable Non-Target Disease Response. Patients who have lesions present at baseline that are evaluable but do not meet the definitions of measurable disease, have received at least one cycle of therapy, and have had their disease re-evaluated will be considered evaluable for non-target disease. The response assessment is based on the presence, absence, or unequivocal progression of the lesions.

24-Month Progression-Free Survival: 24-month PFS is defined as the percentage of patients alive with no evidence of radiological progression per RECIST 1.1 at 24 months from the time of enrollment.

Overall survival: OS is defined as the time from date of enrollment to the date of death due to any cause.

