6.5 Duration of Therapy

In the absence of treatment delays due to adverse event(s), treatment may continue for 4 cycles or until one of the following criteria applies:

- Disease progression (patient will however be monitored for OS)
- Intercurrent illness which would, in the judgment of the investigator, a) affect assessments of clinical status to a significant degree, b) require discontinuation of drug, or c) both a and b
- Unacceptable adverse event(s)
- Delay in treatment of more than 6 weeks.
- Patient decides to withdraw from the study
- General or specific changes in the patient's condition render the patient unacceptable for further treatment in the judgment of the investigator
- Clinical progression
- Patient non-compliance
- Pregnancy
 - All women of child-bearing potential should be instructed to contact the investigator immediately if they suspect they might be pregnant (e.g., missed or late menstrual period) at any time during study participation.
 - The investigator must immediately notify CTEP in the event of a confirmed pregnancy in a patient participating in the study.
- Termination of the study by sponsor

- The drug manufacturer can no longer provide the study agent

The reason(s) for protocol therapy discontinuation, the reason(s) for study removal, and the corresponding dates must be documented in the Case Report Form (CRF).

In April-May 2022 there was a global shortage of Lutetium 177 dotatate. Study enrollment and treatment was held per NCI CTEP's recommendation. The study was not affected as all patients had received cycle 1 of treatment had cleared DLT window. Delay in treatment due to global shortage will not trigger protocol deviation and treatment will resume when drug supply is restored. Patient will then get back on treatment schedule per protocol.

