The MTD will be estimated using isotonic regression based on observed DLT from all patients enrolled in the phase 1 portion and expansion cohort. All patients who received study drugs will be included in the safety analysis. DLTs based on Section 6.2 will be summarized descriptively at each dose level. Adverse events will be summarized based on CTCAE version 5.0. The maximum grade of toxicity for each adverse event category of interest will be recorded for each patient and the summary results will be tabulated by category and grade. We will describe all serious (\geq grade 3) toxicity events on a patient-by-patient basis. Frequency and incidence tables of toxicity and adverse events will be generated in the overall patient group and by dose level depending on patient enrollment.

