9.5 Analysis of Secondary and Correlative Endpoints

ORR will be estimated along with 95% exact binomial confidence interval. PFS and OS will be estimated using the Kaplan-Meier curve and median estimates and confidence intervals will be calculated. Correlative endpoints such as radiographic expression of somatostatin receptors and changes from pre to post-treatment will be summarized using descriptive statistics and changes from baseline *vs.* follow-up time points will be assessed using paired test methodologies. WES data will be processed using the data processing and data analysis pipelines from the Biostatistics and Bioinformatics shared resource of MCC to identify candidate mutated genes with adjustment for false discovery rate. PK analysis will be performed and PK parameters will be estimated from patients enrolled in the dose escalation portion of the phase 1 trial. PK parameters will be compared with historical controls, and exploratorily, we may correlate exposure to toxicity, and incorporate data into a population PK model. Krenning score from the Gallium-68 Dotatate (or Copper-64 Dotatate) will be summarized by calculating the proportion of patients in each Krenning score category and exploratory assessments for association with clinical response (ORR) will be performed using Fisher's exact test. Median, interquartile range will be calculated for quantitative image measurements from Gallium-68 Dotatate (or Copper-64 Dotatate) and exploratory comparison of levels with clinical response (ORR) will be performed using two sample t-test or nonparametric analogs. Mean change in deoxynucleosides between baseline and post treatment samples will be assessed by paired t-test or other methods. Deoxynucleoside plasma concentration as a predictor of clinical outcomes will be explored by linear (progression free survival) and logistic regression (response).

Correlative endpoint analyses will be based on patients who received the RP2D from the dose escalation portion and expansion cohort. See details in Sections 6.3 and 9.4 for RP2D.

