11. STUDY CALENDAR

Baseline evaluations are to be conducted within 30 days prior to start of protocol therapy. Scans and x-rays must be done ≤ 4 weeks prior to the start of therapy. In the event that the patient's condition is deteriorating, laboratory evaluations should be repeated within 48 hours prior to initiation of the next cycle of therapy.

	Screening	Pre-treatment ^a	Cycle 1 (8 weeks)							Cycle 2 (8 weeks)							Cycle 3 (8 weeks)							Disease Progression	Follow-Up and Off-Treatment Visits ^{b,c}			
			Day 1 ^c	Day 9	Day 14 ^c	Day 15 ^c	Day 29 ^c	Day 43 ^c	Days 44-56	Day 1 ^c	Day 14 ^c	Day 29 ^c	Days 30-56	Day 1 ^c	Day 14 ^c	Day 29 ^c	Days 30-56	Day 1 ^c	Day 14 ^c	Day 29 ^c	Days 30-56	Day 1 ^c	Day 14 ^c	Day 29 ^c	Days 30-56			
Triapine			A-----A							A-----A				A-----A			A-----A											
Lutetium Lu 177 Dotataate			B							B				B			B											
Informed consent	X																											
Demographics	X																											
Medical history	X																											
Concurrent meds	X		X-----X																									
Physical exam	X		X				X			X		X		X		X		X		X		X				X		
Vital signs	X		X				X			X		X		X		X		X		X		X				X		
Height	X																											
Weight	X		X				X			X		X		X		X		X		X		X				X		
Performance status ^d	X		X				X			X		X		X		X		X		X		X				X		
CBC w/diff, plts	X		X				X	X	X		X		X		X		X		X		X		X			X		
Comprehensive Chemistry Panel ^e	X		X				X	X	X		X		X		X		X		X		X		X			X		
EKG (as indicated)	X																											

NCI Protocol #: 10388
 Version Date: 17.May.2023

	Screening	Pre-treatment ^a	Cycle 1 (8 weeks)								Cycle 2 (8 weeks)								Cycle 3 (8 weeks)								Disease Progression	Follow-Up and Off-Treatment Visits ^{b,c}
			Day 1 ^c	Day 9	Day 14 ^c	Day 15 ^c	Day 29 ^c	Day 43 ^c	Days 44-56	Day 1 ^c	Day 14 ^c	Day 29 ^c	Days 30-56	Day 1 ^c	Day 14 ^c	Day 29 ^c	Days 30-56	Day 1 ^c	Day 14 ^c	Day 29 ^c	Days 30-56	Day 1 ^c	Day 14 ^c	Day 29 ^c	Days 30-56			
Ga-DOTATATE PET/CT Scan ^f (or 64-Cu DOTATATE PET/CT scan)	X																											
Adverse event evaluation			X-----X																								X	
Radiologic evaluation (CT/MRI Scan) ^g	X ^h		Radiologic measurements should be performed every 8 weeks in the dose escalation cohort. Radiologic measurements should be performed every 12 weeks in the dose expansion cohort.																								X	
Pregnancy test ⁱ	X																											
24-Hour Urine 5HIAA ^j			X																				X ^j		X ^j			

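### Response-evaluable rule in 12.1.1 leaves out patients who progress in Cycle 2, and 9.5 names no ORR denominator to put them back

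*Combined protocol and SAP*

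**What the plan says.** Section 12.1.1 defines who is evaluable for objective response. Patients must have measurable disease at baseline and must "have received at least three cycle of therapy, and have had their disease re-evaluated post-baseline will be considered evaluable for response". One sentence adds patients back: "Patients who exhibit objective disease progression prior to the end of Cycle 1 will also be considered evaluable". The other response set in 12.1.1 is for non-target disease and needs only one cycle. It does not cover measurable disease, which 3.1.4 requires of every patient.

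Section 6.5 allows four cycles unless a stopping criterion applies, the first being "Disease progression (patient will however be monitored for OS").

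Section 9.5 says "ORR will be estimated along with 95% exact binomial confidence interval" and gives no analysis set. The plan does name sets elsewhere. For safety, 9.1 has "All patients who received study drugs will be included in the safety analysis". For correlative work, 9.5 has "Correlative endpoint analyses will be based on patients who received the RP2D from the dose escalation portion and expansion cohort".

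On scan timing, the calendar in Section 11 says "Radiologic measurements should be performed every 12 weeks in the dose expansion cohort". It gives 8 weeks for escalation and a window of 7 days either side (note g). Sections 12 and 12.1 give 8 weeks for everyone. The baseline scan may be up to 4 weeks before treatment (Section 11; 12.1.3).

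**The concern.** Progression in Cycle 1 and progression in Cycle 2 are both treatment failures before three cycles, yet 12.1.1 keeps the first and drops the second. The documents give no reason for the difference. A patient who progresses in Cycle 2 without an earlier response is a known non-responder, and removing that patient from the denominator raises the response rate whenever anyone responds.

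This bears most on the expansion cohort. Best ORR is its response objective (1.2.3), and a first estimate of response is one of its stated purposes (9.1). Response is also the outcome in several correlative analyses in 9.5. For the Krenning score, for example, "exploratory assessments for association with clinical response (ORR) will be performed using Fisher's exact test"; the quantitative imaging and deoxynucleoside analyses use it too. If the 12.1.1 set were carried into those analyses, they would lose the same non-responders.

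**Working it through.** **The plan's own figures.** The plan states no precision for ORR. Its only precision figure is a width of 0.44 for the DLT rate (9.1: n = 17, rate 0.25). The Clopper-Pearson method gives 0.438, so that figure reproduces, but it does not bear on this point.

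**Step 1: the definitions.** A patient who progresses in Cycle 2 and stops under 6.5 has had two cycles, so the three-cycle route fails. Cycle 1 has already ended, so the exception fails as well. This is true whether 'received' means that the third dose was given or that Cycle 3 was completed; 12.1.1 does not say which.

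**Step 2: when the first expansion scan falls.** Cycles are 56 days, so with on-schedule dosing Cycle 1 is Days 1–56 and Cycle 2 is Days 57–112. The calendar does not say where the 12 weeks start. If they start b days before Cycle 1 Day 1, the scan is due on Day 1 + 84 − b, with 7 days either side.

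| b (days) | Due | Window | Window days in Cycle 1 |
|---|---|---|---|
| 0 | 85 | 78–92 | 0 |
| 7 | 78 | 71–85 | 0 |
| 14 | 71 | 64–78 | 0 |
| 21 | 64 | 57–71 | 0 |
| 22 | 63 | 56–70 | 1 |
| 28 | 57 | 50–64 | 7 |

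If week 12 is read as Day 84, the b = 0 window is 77–91. The exception can therefore be reached by a scheduled expansion scan only if the interval runs from a baseline scan 22–28 days before Day 1 and the scan is done early in its window.

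On the 8-week interval of Sections 12 and 12.1, counted from Day 1, the first scan is due on Day 57 (50–64). That window straddles the cycle boundary, so the same progression is kept or dropped according to the scan date.

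**Step 3: effect on ORR.** Let N = 14, R = responders and k = Cycle 2 progressors dropped, all non-responders. ORR moves from R/N to R/(N−k), a factor of N/(N−k): 1.08, 1.17 and 1.40 for k = 1, 2 and 4. R and k are assumptions. R = 2 and R = 4 are close to the response rates quoted in 2.3 (16%; 0.16 × 14 = 2.2) and 2.4 (2% + 28% = 30%; 0.30 × 14 = 4.2). Intervals are Clopper-Pearson.

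| R | k | ORR | Exact 95% CI (%) |
|---|---|---|---|
| 4 | 0 | 4/14 = 28.6% | 8.4–58.1 |
| 4 | 1 | 4/13 = 30.8% | 9.1–61.4 |
| 4 | 2 | 4/12 = 33.3% | 9.9–65.1 |
| 4 | 4 | 4/10 = 40.0% | 12.2–73.8 |
| 2 | 0 | 2/14 = 14.3% | 1.8–42.8 |
| 2 | 1 | 2/13 = 15.4% | 1.9–45.4 |
| 2 | 2 | 2/12 = 16.7% | 2.1–48.4 |
| 2 | 4 | 2/10 = 20.0% | 2.5–55.6 |
| 0 | 0 | 0/14 = 0% | upper limit 23.2 |
| 0 | 2 | 0/12 = 0% | upper limit 26.5 |

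**Step 4: when the direction reverses.** The three-cycle rule also removes patients who stop early for toxicity or withdrawal, and some of them may have responded. If r responders and s non-responders are dropped, ORR rises only if s/r > (N−R)/R. With R = 4 that is 10/4 = 2.5. Dropping one responder gives 3/12 = 25.0% with one non-responder also dropped, 3/11 = 27.3% with two and 3/10 = 30.0% with three, against 28.6% in all 14.

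**The case against.** The case for leaving this alone is mainly about consequence. ORR is secondary, with no test, threshold or decision rule attached. Harm requires that 12.1.1 is used as the denominator, that someone progresses in Cycle 2 and that someone responds. The documents establish none of these. The number dropped is also weakly anchored. Section 2.1 says about 20% of patients do not respond to this therapy, but it neither defines that figure nor ties it to a time. Over a whole course it would be 0.20 × 14 = 2.8 patients, so k = 4 exceeds even that, and k = 0 is possible in a disease that 2.1 calls indolent. The correlative analyses have their own named set. Finally, changing the denominator after accrual has closed is itself a post hoc choice.

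Most of this stands as a limit on size. It justifies treating k = 1–2 as an illustration, k = 4 as an upper bound for display, and the correlative effect as conditional. It does not remove the defect. No section restores Cycle 2 progressors, and a wide interval reflects sampling error, not the selective loss of failures. Leaving 9.5 silent does not avoid a post hoc choice either, because someone must still pick a denominator. Accrual has closed (2.5.2.1), and the investigator and statistician can see the data at all times (13.1).

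**Conclusion.** The concern holds and should be fixed. As written, 12.1.1 leaves Cycle 2 progressors out of the only response-evaluable set for measurable disease, and 9.5 names no other set for ORR. In the expansion cohort, with on-schedule dosing, progression at the first scheduled scan is normally dropped. No earlier scheduled assessment could have shown a response, so these are known non-responders.

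For k = 1–2 and 2 to 4 responders the upward shift is about 1 to 5 percentage points (15.4 − 14.3 = 1.1; 33.3 − 28.6 = 4.7 from the rounded figures). With 4 responders the interval in all 14 is about 50 points wide (58.1 − 8.4 = 49.7). With no responders the estimate stays at 0% and only the upper limit moves. The upward direction is certain for dropped non-responders when there is at least one responder, but not for the net effect of the rule. The size rests on assumed values of k and R; the gap in the definitions does not. The RP2D decision, PFS and OS are unaffected.

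**What to change.** - In 12.1.1 and 9.5, report ORR for each cohort in all treated patients with measurable disease at baseline, counting anyone without a qualifying response as a non-responder. For escalation, use the same set at each time point in 1.2.2. Say whether a qualifying response must be confirmed, since Section 12 and the table in 12.1.4.3 differ on this.
- At minimum, extend the exception to any objective progression before three cycles are received, and define 'received'.
- Keep the three-cycle set as a labelled sensitivity analysis, with the number of patients dropped and the reasons.
- State which set the response-based correlative analyses use.
- State where the scan interval starts, and reconcile the 8-week interval in 12 and 12.1 with the calendar's 12 weeks for expansion.
- Date the change, and say that it was made after accrual closed with data visible to the investigator and statistician.

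The cost is wording and a dated note, with no new data. The reported ORR may turn out lower, unchanged or, if the old rule was dropping a responder, higher.

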12.1.2 Disease Parameters

Measurable disease. Measurable lesions are defined as those that can be accurately measured in at least one dimension (longest diameter to be recorded) as ≥ 20 mm (≥ 2 cm) by chest x-ray or as ≥ 10 mm (≥ 1 cm) with CT scan, MRI, or calipers by clinical exam. All tumor measurements must be recorded in millimeters (or decimal fractions of centimeters).

Note: Tumor lesions that are situated in a previously irradiated area might not be considered measurable.

Malignant lymph nodes. To be considered pathologically enlarged and measurable, a lymph node must be ≥ 15 mm (≥ 1.5 cm) in short axis when assessed by CT scan (CT scan slice thickness recommended to be no greater than 5 mm [0.5 cm]). At baseline and in follow-up, only the short axis will be measured and followed.

Non-measurable disease. All other lesions (or sites of disease), including small lesions (longest diameter < 10 mm [< 1 cm] or pathological lymph nodes with ≥ 10 to < 15 mm [≥ 1 to < 1.5 cm] short axis), are considered non-measurable disease. Bone lesions, leptomeningeal disease, ascites, pleural/pericardial effusions, lymphangitis cutis/pulmonitis, inflammatory breast disease, and abdominal masses (not followed by CT or MRI), are considered as non-measurable.

Note: Cystic lesions that meet the criteria for radiographically defined simple cysts should not be considered as malignant lesions (neither measurable nor non-measurable) since they are, by definition, simple cysts.

‘Cystic lesions’ thought to represent cystic metastases can be considered as measurable lesions, if they meet the definition of measurability described above. However, if non-cystic lesions are present in the same patient, these are preferred for selection as target lesions.

Target lesions. All measurable lesions up to a maximum of 2 lesions per organ and 5 lesions in total, representative of all involved organs, should be identified as **target lesions** and recorded and measured at baseline. Target lesions should be selected on the basis of their size (lesions with the longest diameter), be representative of all involved organs, but in addition should be those that lend themselves to reproducible repeated measurements. It may be the case that, on occasion, the largest lesion does not lend itself to reproducible measurement in which circumstance the next largest lesion which can be measured reproducibly should be selected. A sum of the diameters (longest for non-nodal lesions, short axis for nodal lesions) for all target lesions will be calculated and reported as the baseline sum diameters. If lymph nodes are to be included in the sum, then only the short axis is added into the sum. The baseline sum diameters will be used as reference to further characterize any objective tumor regression in the measurable dimension of the disease.

Non-target lesions. All other lesions (or sites of disease) including any measurable lesions over and above the 5 target lesions should be identified as **non-target lesions** and should also be recorded at baseline. Measurements of these lesions are not required, but the presence, absence, or in rare cases unequivocal progression of each should be noted throughout follow-up.

12.1.3 Methods for Evaluation of Measurable Disease

All measurements should be taken and recorded in metric notation using a ruler or calipers. All baseline evaluations should be performed as closely as possible to the beginning of treatment and never more than 4 weeks before the beginning of the treatment.

The same method of assessment and the same technique should be used to characterize each identified and reported lesion at baseline and during follow-up. Imaging-based evaluation is preferred to evaluation by clinical examination unless the lesion(s) being followed cannot be imaged but are assessable by clinical exam.

Clinical lesions. Clinical lesions will only be considered measurable when they are superficial (e.g., skin nodules and palpable lymph nodes) and ≥ 10 mm (≥ 1 cm) diameter as assessed using calipers (e.g., skin nodules). In the case of skin lesions, documentation by color photography, including a ruler to estimate the size of the lesion, is recommended.

Chest x-ray. Lesions on chest x-ray are acceptable as measurable lesions when they are clearly defined and surrounded by aerated lung. However, CT is preferable.

Conventional CT and MRI. This guideline has defined measurability of lesions on CT scan based on the assumption that CT slice thickness is 5 mm (0.5 cm) or less. If CT scans have slice thickness greater than 5 mm (0.5 cm), the minimum size for a measurable lesion should be twice the slice thickness. MRI is also acceptable in certain situations (e.g. for body scans).

Use of MRI remains a complex issue. MRI has excellent contrast, spatial, and temporal resolution; however, there are many image acquisition variables involved in MRI, which greatly impact image quality, lesion conspicuity, and measurement. Furthermore, the availability of MRI is variable globally. As with CT, if an MRI is performed, the technical specifications of the scanning sequences used should be optimized for the evaluation of the type and site of disease. Furthermore, as with CT, the modality used at follow-up should be the same as was used at baseline and the lesions should be measured/assessed on the same pulse sequence. It is beyond the scope of the RECIST guidelines to prescribe specific MRI pulse sequence parameters for all scanners, body parts, and diseases. Ideally, the same type of scanner should be used and the image acquisition protocol should be followed as closely as possible to prior scans. Body scans should be performed with breath-hold scanning techniques, if possible.

Ultrasound. Ultrasound is not useful in assessment of lesion size and should not be used as a method of measurement. Ultrasound examinations cannot be reproduced in their entirety for independent review at a later date and, because they are operator dependent, it cannot be guaranteed that the same technique and measurements will be taken from one assessment to the next. If new lesions are identified by ultrasound in the course of the study, confirmation by CT or MRI is advised. If there is concern about radiation exposure at CT, MRI may be used instead of CT in selected instances.

Endoscopy, Laparoscopy. The utilization of these techniques for objective tumor evaluation is not

advised. However, such techniques may be useful to confirm complete pathological response when biopsies are obtained or to determine relapse in trials where recurrence following complete response (CR) or surgical resection is an endpoint.

Tumor markers. Tumor markers alone cannot be used to assess response. If markers are initially above the upper normal limit, they must normalize for a patient to be considered in complete clinical response. Specific guidelines for both CA-125 response (in recurrent ovarian cancer) and PSA response (in recurrent prostate cancer) have been published [*JNCI* 96:487-488, 2004; *J Clin Oncol* 17, 3461-3467, 1999; *J Clin Oncol* 26:1148-1159, 2008]. In addition, the Gynecologic Cancer Intergroup has developed CA-125 progression criteria which are to be integrated with objective tumor assessment for use in first-line trials in ovarian cancer [*JNCI* 92:1534-1535, 2000].

Cytology, Histology. These techniques can be used to differentiate between partial responses (PR) and complete responses (CR) in rare cases (e.g., residual lesions in tumor types, such as germ cell tumors, where known residual benign tumors can remain).

The cytological confirmation of the neoplastic origin of any effusion that appears or worsens during treatment when the measurable tumor has met criteria for response or stable disease is mandatory to differentiate between response or stable disease (an effusion may be a side effect of the treatment) and progressive disease.

FDG-PET. While FDG-PET response assessments need additional study, it is sometimes reasonable to incorporate the use of FDG-PET scanning to complement CT scanning in assessment of progression (particularly possible 'new' disease). New lesions on the basis of FDG-PET imaging can be identified according to the following algorithm:

- a. Negative FDG-PET at baseline, with a positive FDG-PET at follow-up is a sign of PD based on a new lesion.
- b. No FDG-PET at baseline and a positive FDG-PET at follow-up: If the positive FDG-PET at follow-up corresponds to a new site of disease confirmed by CT, this is PD. If the positive FDG-PET at follow-up is not confirmed as a new site of disease on CT, additional follow-up CT scans are needed to determine if there is truly progression occurring at that site (if so, the date of PD will be the date of the initial abnormal FDG-PET scan). If the positive FDG-PET at follow-up corresponds to a pre-existing site of disease on CT that is not progressing on the basis of the anatomic images, this is not PD.
- c. FDG-PET may be used to upgrade a response to a CR in a manner similar to a biopsy in cases where a residual radiographic abnormality is thought to represent fibrosis or scarring. The use of FDG-PET in this circumstance should be prospectively described in the protocol and supported by disease-specific medical literature for the indication. However, it must be acknowledged that both approaches may lead to false positive CR due to limitations of FDG-PET and biopsy resolution/sensitivity.

Note: A 'positive' FDG-PET scan lesion means one which is FDG avid with an uptake greater than twice that of the surrounding tissue on the attenuation corrected image.

